3.3.5 Discontinuation of patients from treatment or assessment

3.3.5.1 Criteria for discontinuation

Patients may be discontinued from study treatment and assessments at any time. Specific reasons for discontinuing a patient from this study are:

- Voluntary discontinuation by the patient who is at any time free to discontinue their participation in the study, without prejudice to further treatment
- Safety reasons as judged by the investigator and/or AstraZeneca
- Occurrence of an adverse event, which in the opinion of the investigator warrants the patient's discontinuation. Patients who are discontinued from the study for non-serious or serious adverse events should be followed until the adverse event has been resolved or stabilised and no further change is expected
- If at any time, the patient experiences unexplained muscle pain, tenderness or weakness which is accompanied by CK>10 x ULN, study medication should be discontinued. See management of increased creatine kinase (CK) (Appendix E)
- If ALT (SGPT) is demonstrated to be 3 x ULN on two consecutive occasions >48 hours apart, without obvious reversible precipitating factors, withdrawal of study medication is recommended (see Appendix D)
- Severe non-compliance to protocol as judged by the investigator and/or AstraZeneca (any deviation from the protocol should be reported to the study team who will decide whether the patient should be discontinued from the study)
- Incorrect enrolment (screen failure) i.e., the patient was not randomised as does not meet the required inclusion/exclusion criterion
- Patient lost to follow-up
- Pregnancy
- Deterioration in the patient's condition which in the opinion of the investigator warrants study medication withdrawal.

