3.3.5.2 Incorrectly enrolled or randomised patients

Incorrectly randomised patients will continue to receive study treatment and assessment if, in the opinion of the investigator and/or study team physician, this is not consider to involve any risk or discomfort to the patient. There should be no attempt to switch treatments or change randomisation numbers.

If study medication is contraindicated, incorrectly randomised patients will be discontinue and contact to return study drug. However, the remaining visit and assessments most continue.

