3.3.5.3 Procedures for discontinuation

Patients who discontinue should always be asked about the reason(s) for their discontinuation and the presence of any adverse events. If possible, they should be seen and assessed by an investigator(s). Adverse Events (AEs) should be followed-up. Serious Adverse Events (SAEs)

should be followed-up until resolution or until the patient is lost to follow-up. All investigational products should be returned to the clinic by the patient.

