6.3 Description of analysis sets

Efficacy

Efficacy data will be evaluated based on the intention-to-treat (ITT) and per-protocol (PP) populations.

The ITT population will consist of randomised patients who have a baseline reading and at least one post-baseline reading for at least one efficacy variable, and who have taken at least one dose of study medication. The PP population will consist of all patients in the ITT population who did not have a major protocol violation or deviations that would be likely to affect the efficacy outcomes (i.e. patients taking lipid lowering therapy other tan study drugs).

Patients will be evaluated using randomised treatment/dose (i.e., rosuvastatin 10 mg, rosuvastatin 20 mg, or placebo) for the ITT efficacy analyses, and actual treatment/dose received for the PP efficacy analyses.

For the test of superiority (versus baseline), the ITT population is the primary analysis population. Analyses of the ITT population will be performed using the last observation carried forward (LOCF) method and also using observed data. The LOCF analysis is the primary analysis. LOCF is defined as the last non-missing post-baseline value for a variable carried forward. If no non-missing value exists after baseline, the value will be treated as missing in the analysis. The analyses will be repeated for the PP population as a robustness check using only observed data. Any differences in interpretation of the results from the ITT population will be explored. For tests of no clinically significant deterioration from baseline the ITT and PP populations will be considered equally important.

Safety

The randomised safety population will consist of all patients who were randomised and took at least 1 dose of study medication. Safety data will be evaluated using actual treatment/dose received. In addition safety data from the lead-in period will be evaluated for all patients who enter the lead-in period.

The safety, ITT, and PP populations (including violations and deviations) will be determined prior to treatment unblinding.

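### Section 3.3.5.1 lets non-compliance or a protocol deviation end a patient's assessments; a patient removed this way before visit 3 without a sample is lost from the primary ITT analysis

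*Protocol*

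**What the plan says.** Protocol Section 3.3.5.1 opens with a joint rule: "Patients may be discontinued from study treatment and assessments at any time". Its list of reasons for discontinuing a patient from the study includes "Severe non-compliance to protocol as judged by the investigator and/or AstraZeneca". No threshold is attached. A parenthesis widens the entry: "any deviation from the protocol should be reported to the study team who will decide whether the patient should be discontinued from the study".

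Section 3.3.5.3 asks that a discontinuing patient be questioned about reasons and adverse events, be seen by an investigator where possible, and return the study product. It does not ask for a lipid sample.

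Section 3.3.5.2 treats incorrectly randomised patients differently. Where study drug is contraindicated it is stopped, but then: "However, the remaining visit and assessments most continue" (reading 'most' as 'must').

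Section 6.3 defines the ITT set as "randomised patients who have a baseline reading and at least one post-baseline reading for at least one efficacy variable", with at least one dose taken. LOCF carries forward post-baseline values only, and a patient with none is treated as missing. The LOCF analysis of the ITT set is primary. The PP set is the part of the ITT set without major violations or deviations likely to affect efficacy, and both sets are fixed before unblinding.

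**The concern.** Whether a patient departs from the protocol after randomisation can depend on the assigned arm, for example through tolerability or through persistently high triglycerides. The ITT analysis is meant to be protected from such events, and the PP set is the place where they are dealt with. Section 3.3.5.1 lets the same events also end a patient's assessments, at the discretion of the investigator or sponsor. With a single post-baseline sample, ending assessments early can remove the patient from the ITT set.

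This loss differs from withdrawal of consent or loss to follow-up. The patient may be willing and able to attend visit 3, so the missing value is created by the rule and could be avoided. Because the PP set is drawn from the ITT set, the patient is absent from both, and the PP robustness check cannot reveal the effect of the removal.

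**Working it through.** The protocol gives no figure for this point, so the main check traces the rules. Two short pieces of arithmetic then show what can and cannot be said about size.

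**1. The chain**

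| Step | Source | What follows |
|---|---|---|
| Discontinuation may cover assessments | 3.3.5.1, opening sentence | Removal can end follow-up as well as drug |
| Severe non-compliance is a listed reason; any deviation goes to the study team for a decision | 3.3.5.1 | Removal is discretionary, with no threshold |
| TG and other lipids sampled at visits 1, 2 and 3; apolipoproteins and hsCRP at visits 2 and 3 | 4.7.1.1, 4.7.2.1, 4.7.4.1, Table 1 | Visit 3 is the only scheduled post-baseline reading for every efficacy variable |
| No sample required at discontinuation | 3.3.5.3 | An early leaver may have no post-baseline value |
| ITT needs "at least one post-baseline reading for at least one efficacy variable" | 6.3 | Without a value, the patient is not in the ITT set |
| LOCF uses post-baseline values only | 6.3 | Nothing to carry forward |
| PP is a subset of ITT | 6.3 | The patient is missing from PP too |

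Each step is stated in the text or follows directly from it. Section 6.5 is consistent with this reading, since it equates not completing the 8 weeks with being non-evaluable.

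**2. How many patients could be involved**

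Section 6.5 allows 10 to 15% non-evaluable for all reasons: 330 × 0.10 = 33 and 330 × 0.15 = 49.5, or 11 to 16.5 per arm of 110. Section 3.1 expects 285 to 300 evaluable, which is 30 to 45 lost. The share due to non-compliance is not given, so these figures are only a ceiling on what the plan expects.

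The schedule points to a number well below that ceiling. Drug is dispensed once, at visit 2.1 (Section 3.4.2). No visit is planned between weeks 0 and 8 (Section 3.1), and compliance is checked at visit 3 (Section 3.8), where the fasting sample is also drawn. Missed tablets will usually come to light when the ITT reading is being obtained.

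**3. Direction of bias**

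Let f be the share of an arm removed, K the mean TG reduction in those kept, and R the mean reduction that those removed would have shown. The all-randomised mean is (1 − f)K + fR, so the kept-set mean differs from it by f(K − R). For rosuvastatin against placebo, the shift in the difference is

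f_A(K_A − R_A) − f_P(K_P − R_P).

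- Rosuvastatin patients who stop their tablets: R_A is likely below K_A, so removal enlarges the apparent effect.
- Rosuvastatin patients who add another lipid-lowering drug (the example Section 6.3 gives of a relevant violation): R_A may exceed K_A, so removal shrinks it.
- Placebo patients who add such a drug: R_P is likely above K_P, so removal enlarges it.

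The protocol supplies neither f nor R by arm, so the sign is open and no number follows.

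**4. Why 0.029 and 0.229 do not supply the missing size**

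Section 6.5 labels these values as expected p for two samples. They reproduce the planned 67 per arm when used as proportions (two-sided 5%, 90% power). With p̄ = 0.129 and d = 0.200:

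n = [1.960 × √(2 × 0.129 × 0.871) + 1.282 × √(0.029 × 0.971 + 0.229 × 0.771)]² / 0.200² ≈ 56.9.

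The continuity correction, (n/4)[1 + √(1 + 4/(nd))]², gives 66.6, rounded up to 67. The values therefore act as proportions in the calculation, and Section 6.5 nowhere states a mean placebo reduction of 2.9%.

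**The case against.** The strongest case against is practical. The wording is permissive: patients may be discontinued, and it is the study team "who will decide whether the patient should be discontinued from the study". Reporting a deviation is not removal. Tablet non-adherence is normally discovered at visit 3, when the patient supplies a reading, stays in the ITT set and can be dealt with in PP. A patient who leaves early may be seen by an investigator under Section 3.3.5.3, and Section 4.9 foresees extra samples at unscheduled visits; a lipid value obtained then would count for ITT and LOCF. Decisions are made blind (Sections 3.6.1 and 6.3), which limits deliberate differential removal. All of this stands, and it keeps the likely number small. It does not close the route, because no early sample is required and blinding does not prevent selection on an event that occurs after randomisation.

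A second objection is that Section 3.3.5.2 concerns errors at entry, not conduct afterwards, so the two sections do not contradict each other. That is right. Section 3.3.5.2 serves only to show that the protocol already accepts continued assessment after drug has stopped.

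A third is that the same loss follows any early discontinuation, and that its root is one post-baseline sample combined with an ITT definition that depends on it. That also stands. Non-compliance is singled out because here the loss is a discretionary decision and so can be avoided by changing the rule.

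**Conclusion.** The point holds as a gap in a stated rule. Section 3.3.5.1 permits discretionary post-randomisation removal which, before visit 3 and without a sample, takes a patient out of both the primary ITT analysis and the PP analysis. The number affected is probably small, below a planning ceiling of 10 to 15% for all reasons, and the direction of bias is not determined.

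Two stronger readings are tempting and are not supported:

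- A reader might infer that the ITT analysis becomes an analysis of adherers and that PP becomes nearly identical to it. Removal is optional, and deviations found at visit 3 leave the patient in ITT while still allowing exclusion from PP, so the two sets can differ.
- A reader might take 22.9% and 2.9% as mean reductions, assume 5 to 10% of a rosuvastatin arm is removed with placebo-like change, and conclude that the effect is overstated by 1 to 2 points (0.05 × 20 to 0.10 × 20). The protocol does not give those values as mean reductions, does not give the 5 to 10%, and does not fix the scenario that sets the sign.

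The conclusion assumes that no early sample is taken from the patient concerned. It is worth correcting because the loss is avoidable and the correction is cheap, not because it is expected to change the trial's result.

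**What to change.** In Section 3.3.5.1, state that non-compliance or a protocol deviation does not by itself end assessments. It is recorded as a deviation, the patient is still asked to attend visit 3, and the fasting sample is taken there if the patient consents, following the principle Section 3.3.5.2 already applies to incorrectly randomised patients. Exclusion for the deviation is then left to the blinded PP determination in Section 6.3. Whether study drug is stopped remains a clinical decision and is not touched.

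The cost is a sentence or two in Section 3.3.5.1. Visit 3 and its sample are already scheduled for every randomised patient, so no new procedure, visit or sample is added.

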3.3.5.2 Incorrectly enrolled or randomised patients

Incorrectly randomised patients will continue to receive study treatment and assessment if, in the opinion of the investigator and/or study team physician, this is not consider to involve any risk or discomfort to the patient. There should be no attempt to switch treatments or change randomisation numbers.

If study medication is contraindicated, incorrectly randomised patients will be discontinue and contact to return study drug. However, the remaining visit and assessments most continue.

3.3.5.3 Procedures for discontinuation

Patients who discontinue should always be asked about the reason(s) for their discontinuation and the presence of any adverse events. If possible, they should be seen and assessed by an investigator(s). Adverse Events (AEs) should be followed-up. Serious Adverse Events (SAEs)

should be followed-up until resolution or until the patient is lost to follow-up. All investigational products should be returned to the clinic by the patient.

3.4 Treatments

3.4.1 Identity of investigational product and comparators

AstraZeneca will supply the investigational product. The study medication will consist of tablets of rosuvastatin (Crestor®, AstraZeneca) 10mg, and rosuvastatin 20 mg and tablets of placebo matching 10 and 20 mg of rosuvastatin as shown in Table 2.

Table 2	Dose and strength	
Treatment	Presentation	Strength
Rosuvastatin	Bottle with 100 tabs	10 mg
Rosuvastatin	Bottle with 100 tabs	20 mg
Placebo	Bottle with 100 tabs	Matching 10 and 20 mg

AstraZeneca will package rosuvastatin and placebo by in high-density polyethylene (HDPE) bottles containing 100 tablets and 2 x 1g desiccant.

3.4.2 Doses and treatment regimen

AstraZeneca will provide centres with blinded supplies of study medication. Medication will be dispensed on visit 2.1 on which patients will be given two bottles. Each bottle will contain sufficient tablets and overage to finish study period (see Table 3).

At Visit 2.1 (week 0) following confirmation of eligibility, patients will be randomised to one of three treatment groups; rosuvastatin 10 mg, rosuvastatin 20 mg or placebo. Patients should take two tablets per day at the same day hour during 8 weeks (aprox 2 months). All study medication will be taken orally, with water if required, at any time of day or night.

Table 3Visit schedule

Dispensing Visit	Number of weeks	Number of bottles	Number of tablets per bottle
2.1	8	2	100 (56 days treatment, 2 tablets per day + 44 days overage)

3.4.3 Labelling

All investigational product will be packaged and labeled by AstraZeneca according to local regulatory requirements and in accordance with Good Manufacturing Practice stating that the drug is for clinical use only and should be kept out of the reach of children.

3.4.4 Storage

All investigational products must be kept in a secure place under appropriate storage conditions. A description of the appropriate storage and shipment conditions are specified on the investigational product label and prescribing information (PI). All study drugs will be stored in their original containers (as supplied by AstraZeneca) in a lockable storage facility until dispensed to the patients.

3.4.5 Accountability

It is the investigator/institution's responsibility to establish a system for handling study treatments, including investigational medicinal products, so as to ensure that:

- Accurate records are maintained, accounting for the receipt of the investigational product and for the disposition of the product
- The medication identification number dispensed corresponds to the number allocated by IVRS, prior to treatment dispensation
- Deliveries of such products from AstraZeneca are correctly received by a responsible person (e.g., a study coordinator).
- Study treatments are handled and stored safely and properly and in agreement with the storage instructions printed on the label.
- Study treatments are only dispensed to study patients in accordance with the protocol and are prescribed by the investigator or a person authorised to do so by the principal investigator
- Under no circumstances will the investigator allow the investigational products to be used for other purposes than directed by the protocol.
- It is essential that all medication be accounted for by the investigator or institution, and that any discrepancies are explained and documented. This record keeping consists of a dispensing record including the identification of the person to whom the drug is dispensed, the quantity and the date of dispensing, and any unused drug returned to the investigator. This record is in addition to the drug accountability recorded on the CRFs
- The patient must return all unused investigational products to the investigator. The number of tablets returned must be checked against the number dispensed to

determine patient compliance. Returned and unused product is accounted for and returned to the AstraZeneca Distribution Site for destruction. All returned product should be documented.

3.5 Method of assigning patients to treatment groups

The actual treatment assigned to individual patients will be determined according to a non-centre specific randomisation scheme, which will be produced by AstraZeneca using an AstraZeneca computer software tool, prior to the inclusion of the first patient.

Once a patient has signed the written informed consent form, they will be allocated an enrolment code (e-code) that is a unique identifying number that must be used as the identification number throughout the study. If a patient discontinues from the study, the e-code will not be re-used.

Patients who failed to qualify for the study based on inclusion/exclusion criteria and were not randomised will **not** be allowed to re-enter the study.

The study doctor will establish patient eligibility before treatment randomisation. At Visit 2.1 (Week 0) patients who satisfy the entry criteria will be randomly assigned to receive either rosuvastatin 10 mg, rosuvastatin 20 mg or placebo with a 1:1:1 randomisation ratio. IVRS must be used to randomise the patient. It is important that patients are not randomised ahead of their randomisation visit (Visit 2.1).

At visit 2.1 it is important to check that the medication identification number matches the number allocated by IVRS, prior to treatment dispensation. If a treatment is incorrectly dispensed (i.e., medication identification number does not match the number allocated by IVRS), the error should be rectified and AstraZeneca should be notified as soon as the error is discovered.

3.6 Blinding and Dummy methods and procedures for unbinding the study

3.6.1 Methods for ensuring blinding

The study employs a double blind, double dummy design. Medication for each treatment group will be supplied in identical bottles and will be labelled appropriately so as to maintain the study blind. Patients will receive 2 bottles, and should have on tablet of each bottle as a single dose a day. Patients will receive medication as follows:

- a) For rosuvastatin 10 mg/day treatment arm: 1 bottle of rosuvastatin 10 mg + 1 bottle of placebo, matching rosuvastatin 20 mg.
- b) For rosuvastatin 20 mg/day treatment arm: 1 bottle of rosuvastatin 20 mg + 1 bottle of placebo, matching rosuvastatin 10 mg.

c) For placebo treatment arm: 1 bottles of placebo matching rosuvastatin 10 mg + 1 bottle of placebo, matching rosuvastatin 20 mg.

All study personnel will be unaware of the randomised treatment until all decisions on the evaluability of the data from all patients have been made and documented.

Lipid profile results on visit 1 and 2 will be available for the investigator to made eligibility criteria.

3.6.2 Methods for unblinding the study

The treatment code must not be broken except in medical emergencies when the appropriate management of the patient necessitates knowledge of the treatment randomisation. The investigator(s) must document and report to AstraZeneca any breaking of the treatment code. AstraZeneca retains the right to break the code for SAEs that are unexpected and are suspected to be causally related to an investigational product and that potentially require expedited reporting to regulatory authorities.

If a treatment code is required to be broken, the randomised treatment for each randomised patient will be available to the investigator(s) using IVRS. Routines for this will be described in the IVRS manual that will be provided to each investigational centre.

AstraZeneca will not break treatment codes for the planned analyses of data until all decisions regarding the patients in each patient population have been made and documented.

3.7 Pre-study, concomitant and post-study treatment(s)

Patients must not have been treated with any statin 6 months prior to Visit 1.

Patients must not have been treated with a lipid lowering therapy (other than statin) 6 months before visit 1.

All disallowed medications should be stopped on entry to the study (or 6 months before if it is a lipid-modifying drugs other than statins), and are disallowed during the lead-in period and whilst the patient is receiving study medication. With the exception of lipid-modifying agents (which will affect the study objectives and baseline lipid characteristics), the listed medications are disallowed on the basis of safety concerns. In particular there is a risk of myopathy with antibiotics, antifungals and immunosuppressants (due to possible increases in plasma levels).

Other medication, which is considered necessary for the patient's safety and well being, may be given at the discretion of the investigator(s), provided that they do not conflict with the disallowed medication in Table 4. The administration of all medication (including investigational products) must be recorded in the appropriate sections of the CRF. If antacids are required, they should be taken 2 hours after dosing with study medication.

Class of drug	Generic name
Antibiotics	Erythromycin base, clarithromycin
	Erythromycin ethyl succinate, acetyl sulfisoxazole
Antifungal (chronic systemic use)	Fluconazole
	Ketoconazole
	Itraconazole
Antidiabetics	Insulin
	PPAR α/γ agonists (glitazones)
Lipid regulation	Gemfibrozil
	Fenofibrats
	Benzofibrats
	Niacin
	Ezetimibe
	Atorvastatin
	Lovastatin
	Pravastatin
	Rosuvastatin (except for study medication)
	Simvastatin
	Fluvastatin
	Omega 3
Immunosuppresants	Cyclosporin
	Lymphocyte immune globulin
	Rho(d) immune globulin
	Azathioprine sodium
	Muromonab-CD3
	Prograf (FK-506)
	Cellcept (mycophenolate mofetil)
	Oral or intravenous corticosteroids

Table 4Disallowed concomitant medication

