3.2 Rationale and risk/benefit assessment

3.2.1 Rationale for study design and control group

The NCEP ATPIII recommendations for patients with HTG are first to lower the LDL-C levels and then the TG levels in order to reduce the CV risk(2). In HTG patients, a drug that can reduce both parameters will have an additional benefit.

Statins have been shown convincingly to reduce cardiovascular morbidity and mortality in multiple large outcomes trials in various populations, with substantial reductions in LDL-C and TG levels in non-diabetic and diabetic patients (22, 23). Statins reducing TG levels are known to be directly related to the LDL-C reduction potency meaning that more potent statins should be more effective in lowering TG. For this reason, the current study will use one of the most potent statins (RSV) and will test its efficacy in reducing TG levels in Mexican HTG patients.

This study is using a placebo arm as a control. Patients that are currently on statin therapy cannot enter the study because it would not be ethic to stop their statin therapy. As we are using a placebo arm, the study will only last for 8 weeks and all patients will be treated with TLC diet as appropriate. After completing the study period, all patients will be offer to continue with active commercially available therapy determine by the investigator experience.

The 5-week lead in period will serve as a washout period of possible residual effects of preexisting lipid lowering therapy (other than statins) use, which is important to establish a reliable baseline to determine the change from baseline during double-blind treatment.

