3.3.3 Exclusion criteria

Any of the following is regarded as a criterion for exclusion from the study:

- 1. LDL-C levels \geq 190 mg/dL
- 2. History of any other lipid lowering therapy 6 months before visit 1.
- 3. Subjects considered to be unstable after a myocardial infarction, unstable angina, myocardial revascularisation or a transient ischemic attack (TIA) or stroke
- 4. Subjects awaiting a planned myocardial revascularization prior to starting the study (ie, planned prior to visit 1)
- 5. Severe congestive cardiac failure (New York Heart Association [NYHA] Class IIIb or IV)
- 6. Uncontrolled diabetes diagnosis by $HbA_{1c} \ge 8\%$, or fasten oral glucose $\ge 150 \text{mg/dL}$.
- 7. History of malignancy (unless a documented disease-free period exceeding 5 years is present) with the exception of basal cell or squamous cell carcinoma of the skin. Women with a history of cervical dysplasia would be permitted to enter the study provided they have 3 consecutive clear Papanicolaou (Pap) smears.
- 8. Uncontrolled hypothyroidism defined as a thyroid stimulating hormone (TSH) >1.5 times the upper limit of normal (ULN) at Visit 1. (This is due to the relationship between myopathy and patients with hypothyroidism undergoing statin therapy)
- 9. History of homozygous familial hypercholesterolaemia. (Due to the lipid levels exhibited by this group of patients they are considered unsuitable for this study as they often require combination lipid-lowering therapy)
- 10. History of alcohol, or drug abuse within the last 5 years.
- 11. Current active liver disease [alanine aminotransferase (ALT) (SGPT) > 3 x ULN] or severe hepatic impairment
- 12. Unexplained rise of creatine kinase (CK) \ge 3 x ULN at visit 1

- 13. Serum creatinine > 176 μ mol/L (2.0 mg/dL) at visit 1
- 14. Pregnancy, breast-feeding, and women of childbearing potential who are not using a reliable contraception method.
- 15. Subjects previously screened for this study and/or subjects randomised to treatment who subsequently withdraw cannot re-enter this study.
- 16. Patients participating in any other clinical trial.
- 17. Serious or unstable medical or psychological conditions that, in the opinion of the investigator, would compromise the subject's safety or successful participation in the study.

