3.3.4 Restrictions

Patients must comply with the following restrictions during the study:

- 1. Patients will fast (water is permitted) for 12 hours prior to each visit where lipids are to be measured. Patients should also refrain from consuming alcohol and cigarette smoking on the morning of each of these clinic visits (to obtain accurate and consistent results of lipid measurements).
- 2. Patients should be advised to maintain their normal physical activities or exercise (to avoid the effects of changes in physical activity on laboratory measurements, which may risk observation of spurious rises in CK).
- 3. Patients will be expected to follow the NCEP Therapeutic Lifestyle Changes (TLC) diet for the duration of the study (because dietary intake is known to affect blood cholesterol concentration and thus a standard diet is required in studies of lipid-modifying agents).
- 4. Patients should not receive treatment during the study with any of the disallowed medications outlined in Section 3.7 *(for safety reasons and/or to avoid confounding the study results).*
- 5. Concomitant medication is allowed to treat other problems than HTG such as hypertension, CV disease, DM2 and renal disease.

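### Section 3.7 has all Table 4 drugs stopped on entry, but no eligibility criterion explicitly excludes a patient with an ongoing need for one of the non-lipid drugs (minor patient-safety wording fix)

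*Protocol*

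**What the plan says.** Section 3.7 sets the rule: "All disallowed medications should be stopped on entry to the study (or 6 months before if it is a lipid-modifying drugs other than statins"). The ban runs through the lead-in and the treatment period. Lipid-modifying agents are banned because they would disturb the study objectives and the baseline; for the rest, "the listed medications are disallowed on the basis of safety concerns". The investigator may give other medication needed for the patient's safety, but only "provided that they do not conflict with the disallowed medication in Table 4". Section 3.3.4 item 4 repeats the ban: "Patients should not receive treatment during the study with any of the disallowed medications outlined in Section 3.7". Item 5 of the same list then says: "Concomitant medication is allowed to treat other problems than HTG such as hypertension, CV disease, DM2 and renal disease".

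For lipid drugs, eligibility does the work. Inclusion 3 and 4 and exclusion 2 require 6 months without them. Section 3.2.1 gives the reason for keeping current statin users out: "Patients that are currently on statin therapy cannot enter the study because it would not be ethic to stop their statin therapy".

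The diabetes criterion, exclusion 6 in 3.3.3, begins "Uncontrolled diabetes diagnosis by" and is defined by laboratory values (HbA1c of 8% or more, or fasting glucose of 150 mg/dL or more), not by treatment.

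**The concern.** Two kinds of prohibited drug are handled in opposite ways. A patient on a statin is kept out, so that the therapy is not interrupted for the trial's sake. A patient on insulin, azathioprine or long-term corticosteroids meets no criterion that mentions the drug, and the only direct instruction to the site is to stop it. The protocol does not say how to stop it (no taper), nor that a needed drug should be left alone. Section 3.7.1.1 shows that drug-specific handling could be written: it gives monitoring instructions for vitamin K antagonists.

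What is at stake is patient safety and clear eligibility, not inference. Most of Table 4 is there to protect patients, and withdrawing necessary therapy so that someone can enter the study works against that purpose.

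**Working it through.** The check is mainly a comparison of sections, with some arithmetic on timing and screening.

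1. **Scope of Table 4.** It has five classes. As laid out, lipid regulation has 12 entries. The four non-lipid classes have 2 (antibiotics) + 3 (antifungals) + 2 (antidiabetics) + 8 (immunosuppressants) = 15. These are table rows, not a measure of how many patients take the drugs.

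2. **Eligibility criteria that name a Table 4 drug class.** Of the 9 inclusion criteria, items 3 and 4 concern drug history, both for lipid therapy. Of the 17 exclusion criteria, item 2 does, again for lipid therapy. Criteria naming a non-lipid Table 4 drug: 0 of 9 and 0 of 17.

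3. **Does exclusion 6 catch the diabetic patients?** Only if control is poor. A patient held below both thresholds by insulin or a glitazone passes. Table 1 schedules HbA1c at Visit 1 only, so it reflects control before any stop at that visit.

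4. **Indirect routes.** Exclusion 17 lets the investigator exclude a condition that is serious or unstable and would endanger safety or participation. Inclusion 9 requires willingness to follow the study procedures, and 3.3.4 makes avoiding Table 4 drugs an obligation, so a patient who cannot give up such a drug can be judged unable to comply. Neither names a drug; the first is discretionary and the second has to be inferred.

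5. **Substitution.** Section 3.7 allows necessary drugs that are not in Table 4, and 3.3.4 item 5 allows treatment of type 2 diabetes. A switch to an unlisted drug is therefore permitted. What remains is the missing taper instruction and any drug without a practical substitute.

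6. **Timing.** Visit 1 is at week -5 and Visit 2 at week -1: 4 × 7 = 28 days. Table 1 schedules no clinic visit or glucose test in between. Section 3.1 gives ±3 days for each of the two visits, while Table 1 leaves the Visit 1 cell blank. If both windows apply to planned dates, the interval runs from 28 − 6 = 22 to 28 + 6 = 34 days; if Visit 1 is the anchor, from 25 to 31. Notes in 3.1 and 3.3.2 confirm that the Visit 1 triglyceride and LDL-C results are not available when the patient enters the lead-in.

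7. **Who would be exposed to the stop instruction.** The plan expects 330 × 3 = 990 lead-in entrants, which reproduces its figure. Then 990 − 330 = 660, and 660/990 is about 67%. If that ratio also held for users of these drugs (an assumption), about two in three of those told to stop would never be randomised. The protocol does not say how many take such a drug.

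**The case against.** The strongest reply is that no sensible investigator would withdraw needed insulin or transplant immunosuppression to fill a trial place, and that the protocol gives enough cover. Exclusion 17 applies to conditions that are serious or unstable, so a stable but serious illness qualifies. Inclusion 9 with 3.3.4 points the same way. Section 3.7 says these drugs should be stopped, while its 6-month lipid rules use must. Informed consent, GCP and discontinuation for safety (3.3.5.1) all apply. Patients who fail the Visit 1 lipid criteria are contacted and discontinued. Glucose is measured again at Visit 2, with eligibility rechecked under Table 1 note e. Serious adverse events are recorded from consent.

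Much of this stands, and it lowers the severity. It does not remove the point. The indirect routes depend on individual judgement, and discontinuation or a later glucose test acts only after the drug has been stopped.

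A reader might infer more than the text supports:

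- **That nothing can keep these patients out.** Not so; the routes in step 4 exist, though none is explicit.
- **That substitution is ruled out.** Not so; unlisted drugs are allowed.
- **That items 4 and 5 of 3.3.4 contradict each other.** Item 4 stands directly above item 5, and the Table 4 proviso in 3.7 says how they fit together: diabetes drugs in general are allowed, the listed ones are not. Item 5 could be clearer, but this is not a real conflict.
- **That the efficacy comparison is biased.** Any stop on entry comes before randomisation and applies to all arms alike, so the comparisons with placebo in 6.4.1.1 are not biased by it.

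**Conclusion.** The point holds as a minor patient-safety wording fix. A stated rule, followed literally, would stop a needed non-lipid drug at Visit 1. No criterion explicitly prevents this, and it departs from the principle that 3.2.1 applies to statin users. The gap to the next scheduled visit and glucose test is about 4 weeks (nominally 28 days, before visit windows).

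This rests on a literal reading of 3.7 and on the existence of candidates who are well controlled on such a drug. The protocol foresees medicated patients with type 2 diabetes but gives no count of those on a Table 4 drug, so no number of affected patients can be stated. Sample size and power are unchanged.

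**What to change.** 1. Add to 3.3.3: *Ongoing need for a non-lipid drug listed in Table 4 (for example insulin, a glitazone, a maintenance immunosuppressant, long-term oral or intravenous corticosteroids, or a chronic systemic antifungal).*
2. In 3.7, state that such a drug is not to be stopped in order to enter the study, and that a short course of a Table 4 drug, such as an antibiotic, is to be finished before Visit 1. The timing matters because of exclusion 15: "Subjects previously screened for this study and/or subjects randomised to treatment who subsequently withdraw cannot re-enter this study". Keep the 6-month rule for lipid drugs.
3. Optionally, for clarity only, add *except drugs listed in Table 4* to 3.3.4 item 5.

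The cost is a wording amendment and slightly more screen failures, identifiable from the medication history already taken at Visit 1. At the planned ratio, each excluded lead-in entrant costs on average 330/990, about one third of a randomised patient, assuming such patients would otherwise be randomised at the average rate. The total cannot be derived from the protocol.
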